## 2. Aims and objectives

### Primary objective:

To determine whether mental wellbeing as measured by the SF-36 (mental health dimension) six months after randomisation is significantly increased in participants allocated to receive the telephone friendship group intervention compared to participants allocated to a control group (receiving only contact by card/letter or telephone at month 2, 4, 8 and 10 with no further contact other than follow up assessment). This will necessitate taking the following three factors into account: (1) participants are randomised between zero and two months before a telephone friendship group is ready for them to join; (2) the intervention may last between four and five months; (3) control arm participants get no protocol-specified intervention. The choice of six months follow-up for the primary outcome makes it likely that the intervention will have been completed, or at least will be well underway and have delivered a 'therapeutic dose'. The time point means that everyone (intervention arm, however close to start of intervention they were randomised; and, control arm) are assessed at the same point from randomisation.

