#### **Study reminder (2 and 4 months)**

All participants will receive a **Contact card (17)** by post from the research team, at 2 and 4 months. The brief card will thank the participant, provide an update on progress and a reminder that we will be in touch again in another 2 months.

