### **Procedures for attempted follow-up of participants “lost to follow-up”**

Participants will be considered lost-to-follow-up if they fail to respond to three telephone messages and one reminder letter. A minimum of six calls will be made to candidates where there is no facility to leave a message. If the candidate has provided an email address, the research team will also attempt to make contact via this method. For those participants previously identified (at earlier points in the study) as requiring assistance, an additional telephone call will be made. There are no procedures for further follow-up.

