### **Procedures required to record (serious) adverse events**

In line with previous studies which deliver interventions to promote self-efficacy, we do not anticipate adverse events associated with the research interventions. Four categories of serious adverse events (SAEs) will be recorded during follow-up: results in death; is life-threatening; requires hospitalisation (initial or prolonged); results in persistent or significant disability or incapacity. The collection and reporting of SAE data will be governed by Sheffield CTRU standard operating procedures.

At each follow-up (as described above), participants will be asked if they have experienced any event or illness in the last six months which:

- has required unscheduled hospitalisation; or,
- has resulted in persistent or significant disability / incapacity (see appendix 2).

Information obtained from the NHS Health and Social Care Information Centre will be used to inform the collection and reporting of SAEs, where appropriate.

*It is the Chief Investigator's responsibility:*

1. To follow the procedure outlined in the study protocol for the reporting of SAEs;
2. To assess each event for causality and AE category;
3. To provide the Dean of SchARR and the University Research Office (in their capacity as representatives of the sponsor) with details of all SAEs identified within agreed timeframes;
4. To notify the Trial Steering Committee and Data Monitoring and Ethics Committee of any SAEs where appropriate; and,
5. To submit the annual safety report to the REC.

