## 9. Statistics

### Sample Size

For the purposes of sample size estimation the primary outcome will be the mean SF-36 mental health (MH) dimension score at six-months post randomisation. The SF-36 mental health dimension is scored on a 0 (poor) to 100 (good health) scale. A previous general population survey of Sheffield residents has demonstrated that the SF-36 can successfully be used as an outcome measure for community dwelling residents aged 75 or more where a response rate of 82% was achieved (Walters et al 2001). From this general population survey of 3,084 Sheffield community residents, the mean SF-36 mental health score was 68.3 with a standard deviation of 19.9 (Walters et al 2001).

The developers of the SF-36 have suggested that differences between groups of between 5 and 10 points on the 100-point scale can be regarded as “clinically and socially relevant” (Ware et al 1993). If we assume a standard deviation of 20 points for the SF-36 Mental health score at six months post randomisation and that a mean difference in MH scores between the intervention and control group of 8 or more points is the smallest difference that can be regarded as clinically and practically important. We are going to analyse the six-month outcome data with a multiple regression/analysis of covariance model (ANCOVA) model with baseline score as a covariate. We shall assume a correlation of 0.50 between the baseline and six-month mental health score. Then to have an 90% power of detecting this 8-point mean difference in MH scores at six months between the Intervention and controls as statistically significant at the 5% (two-sided) level will require 99 patients per group (2 x 99 = 198 in total).

However, the telephone befriending intervention is a group or facilitator-led intervention. Therefore the success of the intervention may depend on the facilitator delivering it so that the outcomes of the participants in the same group with the same facilitator may be clustered. If we assume an average cluster size of 6 subjects per telephone befriending group and an intra cluster correlation (ICC) of 0.04, then the design effect is 1.28. With these assumptions and 99 subjects per group the power of the analysis is reduced to 80% to detect a mean difference of eight points in six-month MH scores. If 20% of participants drop out and are lost to follow-up then we will need to recruit and randomise 124 per group (248 in total).

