Appendix 1: Revised CONSORT 2010 Flow Diagram

Appendix 2: Serious Adverse Event Checklist (6 month and 12 month follow-up)

DETAILS:

\* If details are unclear was permission granted to contact GP for verification and/or confirmation?

Yes  No

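### A fixed six-month look-back in the SAE question leaves part of follow-up unasked whenever a follow-up contact is missed or late

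*Protocol*

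**What the plan says.** Protocol Section 8, on recording (serious) adverse events, fixes the SAE question: at each follow-up, "participants will be asked if they have experienced any event or illness in the last six months which" led to unscheduled hospitalisation or to lasting disability or incapacity. One form serves both occasions ("Appendix 2: Serious Adverse Event Checklist (6 month and 12 month follow-up"). Section 8 lists it only among the six- and twelve-month procedures.

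The contacts in between are postal cards at months 2, 4, 8 and 10. They are described as thanks, news and a reminder ("The brief card will thank the participant, provide an update on progress and a reminder that we will be in touch again in another 2", the unit being months), with no SAE question.

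The Primary objective gives the timing of exposure: "participants are randomised between zero and two months before a telephone friendship group is ready for them to join", and "the intervention may last between four and five months".

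On losses, the Sample Size section says "If 20% of participants drop out and are lost to follow-up then we will need to recruit and randomise 124 per group", and the Stopping rules place the anticipated 20% loss at six months. The procedures for attempted follow-up say "Participants will be considered lost-to-follow-up if they fail to respond to three telephone messages and one reminder letter", and state that no further follow-up steps exist. They do not say whether someone missed at month 6 is tried again at month 12. The protocol gives no visit window for either contact.

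**The concern.** Two six-month windows tile the year only if both contacts happen, and happen at months 6 and 12. Nothing in the text lengthens the look-back after a missed or late contact. The protocol itself plans for a fifth of participants to have no six-month outcome.

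The period most exposed to the gap is months 0-6, which holds most or all of the intervention. The protocol sets no statistical stopping criteria and leaves any safety decision to the steering committee or funder on the monitoring committee's advice, so the SAE record is the material that such advice would use. Participants are aged 75 and over, and illness or a hospital stay is a plausible reason for a missed or delayed contact. The events left unasked may therefore be among those the checklist is meant to find.

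**Working it through.** **Planned loss.** Inflating 99 per group for 20% loss gives 99 / (1 - 0.20) = 123.75, so 124 per group and 248 in total. This reproduces the protocol's figure. Participants without a six-month contact: 124 - 99 = 25 per arm, about 50 overall (0.20 x 248 = 49.6).

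**Set-up.** Time is in months from randomisation. Let w be the wait (0 to 2) and L the duration of the intervention (4 to 5), both from the Primary objective. The intervention is taken to run from w to w + L. A contact at time t asks about t - 6 to t.

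**Both contacts on time.** The windows are 0-6 and 6-12. Nothing is unasked.

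**Month 6 missed, month 12 on time.** The only window is 6-12, so months 0-6 are unasked. Share of the intervention unasked = (min(6, w + L) - w) / L.
- If w + L is 6 or less (all 4-month interventions, and 5-month interventions with a wait of up to 1 month), the share is 100%.
- With w = 2 and L = 5 the intervention runs from 2 to 7, and the share is (6 - 2) / 5 = 80%. This is the minimum over the stated ranges.

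**Month 6 late by d, month 12 on time.** The windows are d to 6 + d, and 6 to 12. The first d months after randomisation are unasked. Share of the intervention unasked = max(0, d - w) / L. The protocol states no delays, so the values of d are assumptions.

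| Wait w | d = 1 | d = 2 | d = 3 |
|---|---|---|---|
| 0 | 20-25% | 40-50% | 60-75% |
| 1 | 0% | 20-25% | 40-50% |
| 2 | 0% | 0% | 20-25% |

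In each cell the lower figure is for L = 5 and the higher for L = 4.

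**Month 6 on time, month 12 late by e.** The second window is 6 + e to 12 + e, so months 6 to 6 + e are unasked. This lies after the intervention unless w + L exceeds 6. With w = 2, L = 5 and e = 1 it removes month 6-7, or 1 / 5 = 20% of the intervention.

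**With an anchored prompt.** If each contact asks about the whole time since randomisation or since the last completed checklist, the unasked share is 0% in every case above, provided that a later contact is completed.

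**The case against.** **Those lost at month 6 may never be contacted again.** The follow-up procedures can be read that way, and then nobody falls between the two windows and new wording alone helps none of them. The text does not settle it. The cards at months 8 and 10 go to all participants and promise further contact, and the withdrawal procedures continue follow-up unless consent to it is explicitly withdrawn. Both point towards an approach at month 12. The gap from late contacts exists on either reading.

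**There are other routes to SAEs.** Section 8 brings in information from the NHS Health and Social Care Information Centre where appropriate, and the resource use questionnaire covers secondary care. These count, but only in part. Section 7 describes the central data as showing health status and avoiding contact with people who have died; it does not say that they recover hospitalisation or disability. The questionnaire's look-back is not stated. Unit procedures also govern SAE collection. They are not shown, but the protocol itself states the recall period.

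**A fixed look-back gives every respondent the same recall period.** This is a genuine advantage, and the change gives some of it up.

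A reader might infer more than the documents support:
- *That about 50 participants are affected by the wording.* The 50 lack a month-6 contact. The wording matters only for those who return at month 12. All 50 returning is not realistic, because the protocol foresees deaths and withdrawals.
- *That a late contact can lose all of the intervention period.* Delay reaches the intervention only beyond the 0-2 month wait. Losing all of it would need a delay of at least w + L, which is four months or more.
- *That a planned comparison of SAEs between arms is biased.* Section 9 states no such comparison, and a difference in non-response between arms is conjecture.
- *That events will be counted twice.* A late month-6 contact followed by an on-time month-12 contact does give overlapping windows. Whether an event is then counted twice depends on whether the checklist records dates, and its content is not visible.

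**Conclusion.** The concern holds in a limited form. As worded, the SAE question covers 12 months only if both contacts are made on time. For a participant missed at month 6 and reached at month 12, months 0-6 go unasked, including 80-100% of the intervention period for those allocated to it. For a late month-6 contact the loss is the first d months after randomisation, with nothing lost from the intervention unless d exceeds the wait. A late month-12 contact leaves a gap after month 6.

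The number affected cannot be derived from the protocol. About 25 per arm are expected to miss month 6, and those later reached at month 12 are an unknown subset, possibly none. The percentages assume that the 4-5 months run from the end of the 0-2 month wait. If the introductory calls begin during the wait, the intervention falls earlier: more of it then lies in months 0-6, and a shorter delay would reach it. The protocol regards the intervention as low risk and expects no related adverse events, so this is a gap in safety recording and does not threaten the primary analysis. It is worth correcting because the correction is nearly free.

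**What to change.** 1. In the Section 8 text on adverse events and in the Appendix 2 checklist, replace the fixed look-back. At the first completed contact ask about events *since you joined the study*. At any later contact ask about events *since we last completed this checklist with you on [date]*.
2. Make sure that the checklist records the date of each event, if it does not already, so that each can be placed in time and counted once.
3. In the procedures for attempted follow-up, state that a participant missed at six months is still approached at 12 months unless consent to follow-up has been withdrawn. Without this, the new wording cannot help those who missed month 6.

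The cost is a change of wording on an existing form, possibly a date field, and one sentence on follow-up; no visit is added. The drawback is that participants who missed month 6 must recall up to 12 months. That is less reliable than six-month recall, and recall periods will differ between participants, but it is better than no enquiry about the first six months.

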## 9. Statistics

### Sample Size

For the purposes of sample size estimation the primary outcome will be the mean SF-36 mental health (MH) dimension score at six-months post randomisation. The SF-36 mental health dimension is scored on a 0 (poor) to 100 (good health) scale. A previous general population survey of Sheffield residents has demonstrated that the SF-36 can successfully be used as an outcome measure for community dwelling residents aged 75 or more where a response rate of 82% was achieved (Walters et al 2001). From this general population survey of 3,084 Sheffield community residents, the mean SF-36 mental health score was 68.3 with a standard deviation of 19.9 (Walters et al 2001).

The developers of the SF-36 have suggested that differences between groups of between 5 and 10 points on the 100-point scale can be regarded as “clinically and socially relevant” (Ware et al 1993). If we assume a standard deviation of 20 points for the SF-36 Mental health score at six months post randomisation and that a mean difference in MH scores between the intervention and control group of 8 or more points is the smallest difference that can be regarded as clinically and practically important. We are going to analyse the six-month outcome data with a multiple regression/analysis of covariance model (ANCOVA) model with baseline score as a covariate. We shall assume a correlation of 0.50 between the baseline and six-month mental health score. Then to have an 90% power of detecting this 8-point mean difference in MH scores at six months between the Intervention and controls as statistically significant at the 5% (two-sided) level will require 99 patients per group (2 x 99 = 198 in total).

However, the telephone befriending intervention is a group or facilitator-led intervention. Therefore the success of the intervention may depend on the facilitator delivering it so that the outcomes of the participants in the same group with the same facilitator may be clustered. If we assume an average cluster size of 6 subjects per telephone befriending group and an intra cluster correlation (ICC) of 0.04, then the design effect is 1.28. With these assumptions and 99 subjects per group the power of the analysis is reduced to 80% to detect a mean difference of eight points in six-month MH scores. If 20% of participants drop out and are lost to follow-up then we will need to recruit and randomise 124 per group (248 in total).

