### Analysis of primary objective

As the trial is a pragmatic randomised, with a usual (control) treatment arm, data will be reported and presented according to the revised CONSORT 2010 statement (Schultz et al, 2010). The statistical analysis will be performed on an intention-to-treat-basis.

All statistical exploratory tests will be two-tailed with  $\alpha = 0.05$ . Baseline demographic (age, gender) and person reported outcome measures (PROM) data (SF-36, PHQ-9, EQ-5D, GSE, de Jong Loneliness Scale, 6CIT) will be assessed for comparability between the groups.

The aim of the analysis will be to establish firstly whether there are benefits from a telephone friendship intervention compared with the control group. Since the intervention, the telephone friendship group, is a group or therapist based intervention, there may be clustering or correlation of the participants' outcomes within a telephone befriending group. Therefore to make allowance for this the primary analysis will compare mean SF-36 Mental Health dimension scores at six months between the intervention group and control group using a marginal general linear model (GLM), with robust standard errors, and an exchangeable correlation (Walters, 2009). The marginal model will use Generalised Estimating equations (GEE) to estimate the regression coefficients. Participants in the control group will be treated as clusters of size one in the analysis. The exchangeable correlation assumes that participant outcomes within each cluster (telephone befriending group) have the same correlation. A 95% confidence interval (CI) for the treatment group coefficient, the difference in SF-36 mental health dimension scores between the intervention and control group, will also be calculated. An adjusted analysis will also be performed alongside this unadjusted analysis which will include baseline covariates, such as age, gender and baseline SF-36 mental health score in the marginal general linear model.

For the primary outcome, the SF-36 Mental Health dimension score at six months follow-up, missing data will be imputed through a variety of methods, including Last Observation Carried Forward (LOCF), regression and multiple imputations.

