### 10.2 Fidelity assessment sub-study (facilitators)

The fidelity assessment will assess how well the telephone friendship intervention is delivered according to the intervention protocol (see Section 7). An intervention fidelity framework based on that identified by the Behaviour Change Consortium (Bellg et al, 2005) has been developed (Table 1). The framework sets out the parameters by which quality and fidelity will be measured according to study design, training, delivery, receipt and enactment.

Facilitator attendance at facilitator training sessions will be monitored by a **training attendance register** (not submitted to REC) taken by a single trainer ([name], Community Network) who will train all facilitators to measure 'treatment dose'. The trial manager (RG-W) and content expert (MC) will observe a sample of training sessions (at least one per cycle) and use a **training content checklist** (not submitted to REC) to assure consistency of materials and practice by the trainer as well as to confirm facilitator skill acquisition.

Attendance at group befriending sessions will be monitored by the use of **participant attendance registers** (not submitted to REC) taken by the facilitators at every session during both the one-to-one and group phases.

A random sample of thirteen (5%) audio recordings of group sessions will be taken. Permission to audio record group sessions will be obtained via the **Participant Consent Form (7)** and again at the start of a group session that has been selected. The trial manager (RG-W) and content expert (MC) will use a **facilitator checklist** (not submitted to REC) to assess:

- The match with the intervention protocol, in terms of the content and techniques delivered;
- The extent to which facilitators have enabled choice and decision-making;
- “Drift” in facilitation skills and intervention delivery (for those facilitating groups across successive waves / cycles) with information on adherence being fed back to facilitators as necessary.

The group facilitation skills of individual volunteer facilitators will be self-assessed, with facilitators recording any difficulties with the delivery of the intervention protocol in a **facilitator diary** (not submitted to REC).

The **General Perceived Self Efficacy (GSE) Scale (11)** and **de Jong Gierveld Loneliness Scale (12)** will be used to test the extent to which baseline loneliness and self-efficacy affect all outcomes at follow-up.

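### Protocol section 9 states a design effect of 1.28 where its own inputs give 1.20, so the stated 80% power does not follow; under the ANCOVA assumptions the error is conservative

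*Protocol*

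**What the plan says.** Protocol section 9, Sample Size, builds the target in three steps.

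- **Individual-level calculation.** The authors "assume a standard deviation of 20 points for the SF-36 Mental health score at six months post randomisation" and a baseline to six-month correlation of 0.50, for an ANCOVA with baseline score as covariate. The target is 8 points. They want "to have an 90% power of detecting this 8-point mean difference in MH scores at six months", which as "statistically significant at the 5% (two-sided) level will require 99 patients per group".
- **Clustering.** Because the intervention is delivered in facilitated groups, the section takes an average of "6 subjects per telephone befriending group and an intra cluster correlation (ICC) of 0.04, then the design effect is 1.28". It continues: "With these assumptions and 99 subjects per group the power of the analysis is reduced to 80" per cent for the same 8 points.
- **Dropout.** A 20% loss takes 99 to 124 per arm, 248 in total.

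The section does not say which arms the design effect applies to. Its reason for clustering concerns only the group-delivered intervention. Under Analysis of primary objective, the GEE model has no clustering among controls: "Participants in the control group will be treated as clusters of size one in the analysis". That section also describes the main comparison as unadjusted, with an adjusted analysis run alongside it. The Trial Summary, by contrast, says that the marginal model will include baseline covariates.

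The 80% figure is repeated in the Trial Summary and under Stopping rules (section 3).

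**The concern.** The cluster size, the ICC and the design effect stand in one sentence and cannot all be right under the standard formula. The power quoted next depends on that design effect, and it is the stated justification for 248. A reader who tries to reproduce the 80% has to use the wrong design effect and also inflate a control arm that the analysis treats as independent.

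What is at stake is whether the power claim can be relied on and reproduced. Stopping rules also commits the trial to a sample-size re-calculation from the pilot SD, correlation and ICC. That exercise must turn an ICC into a variance inflation, so the conversion and the arms it applies to should be settled beforehand.

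**Working it through.** **Inputs** (all from section 9, Sample Size, except the last): difference 8; SD 20; correlation 0.50; two-sided 5%; 99 per arm; 6 per group; ICC 0.04; 20% loss; controls as clusters of size one (Analysis of primary objective).

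**1. Reproduce the unclustered figure.** Residual variance = 20² × (1 − 0.50²) = 300, so the residual SD is 17.32. For 90% power, n = 2 × 300 × (1.960 + 1.282)² / 8² = 98.5, that is 99 per arm. This reproduces the protocol. So does the dropout step: 99 / 0.8 = 123.75, that is 124 per arm and 248 in total.

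**2. Design effect.** DE = 1 + (m − 1) × ICC.

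- m = 6, ICC 0.04: 1 + 5 × 0.04 = **1.20**.
- For 1.28 at ICC 0.04: m = 1 + 0.28 / 0.04 = 8.
- For 1.28 at m = 6: ICC = 0.28 / 5 = 0.056.

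**3. Power at 99 per arm, ANCOVA.** SE = √(300 × (DE_int + DE_con) / 99); power = Φ(8 / SE − 1.960).

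| DE intervention | DE control | SE | Power |
|---|---|---|---|
| 1 | 1 | 2.462 | 90.1% |
| 1.28 | 1.28 | 2.785 | 81.9% |
| 1.28 | 1 | 2.628 | 86.1% |
| 1.20 | 1.20 | 2.697 | 84.3% |
| 1.20 | 1 | 2.582 | 87.3% |

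Of the rows with clustering, only the second comes within two points of the stated 80%. Changing the group size to 8 would repair the 1.28 but not the 80%: with controls unclustered, power is still 86.1%.

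**4. The same without the baseline adjustment.** With variance 400 in place of 300 and 1.20 in the intervention arm only, SE = √(400 × 2.20 / 99) = 2.981 and power = Φ(8 / 2.981 − 1.960) = 76.5%, about 77%. With 1.20 in both arms it is about 73%.

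**5. Sensitivity to the number of groups.** 99 / 6 is 16 to 17 intervention groups. A t reference on 15 to 16 degrees of freedom, which the protocol does not specify, gives about 83% for the ANCOVA with 1.20 in one arm, and 79 to 80% with 1.20 in both.

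**The case against.** The strongest reply is that nothing is harmed. On the ANCOVA assumptions the true power is above the stated 80%, recruitment need not change, and no analysis changes. That stands, and it limits the point to an error in the justification.

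It can also be said that 1.20 is exact only for groups of equal size. The unequal-size form, 1 + ((1 + CV²) × 6 − 1) × 0.04, reaches 1.28 at a CV of about 0.58, and the protocol expects variable attendance and some participants who never join a group. But the protocol states no CV and mentions no such allowance, so this does not rescue the figure. It is a reason to state the equal-size assumption. Similarly, a small-sample reference would bring power nearer 80%, but none is stated.

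Four stronger readings are tempting, and the document does not support them.

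- **That both arms were inflated, as a fact.** The text does not say so. It is an inference from the 80%, and even then the result is 81.9%.
- **That 1.28 will pass into the re-calculation.** Stopping rules names the SD, the correlation, the ICC and the 8-point difference, but no design effect or cluster size.
- **That the fidelity sample settles the group size at 6.** Section 10.2 says "A random sample of thirteen (5%) audio recordings of group sessions will be taken". Groups of 6 would give 124 / 6 × 12 × 0.05 = 12.4 recordings. But 5% of 248 participants is also 12.4, and the section states no number of sessions or groups.
- **That recruitment could be cut.** The surplus over 80% depends on the adjusted model being primary, on equal group sizes and on large-sample tests.

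**Conclusion.** The point holds. The design effect should read 1.20 for the stated group size and ICC, and the stated 80% does not follow from the protocol's inputs. With 1.20 in the intervention arm only, as the analysis model implies, large-sample power at 99 per arm is about 87%; it is about 84% if both arms are inflated. The protocol therefore understates its power under the ANCOVA assumptions, and 248 is not too small. A reader who sees a wrong power figure might infer an underpowered trial, but this error does not show that.

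The 87% cannot stand as an unqualified headline. It rests on SD 20, correlation 0.50, equal groups of 6, a normal reference distribution and a baseline-adjusted primary model. The Sample Size section and the Trial Summary point to that model, but Analysis of primary objective calls the main comparison unadjusted. On that reading power is about 77%, below the target. That is a consequence of which model is primary, separate from the design-effect error.

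**What to change.** 1. In section 9, Sample Size, correct the design effect to 1.20. If groups of 8 are intended, change the 6 to 8 and keep 1.28; the adjusted power is then about 86%. State that the inflation applies to the intervention arm only.
2. Reconcile Sample Size with Analysis of primary objective on which model is primary. The baseline-adjusted model is the one that matches the sample-size calculation.
3. Restate the power in Sample Size, the Trial Summary and Stopping rules for that named model: about 87% if adjusted, about 77% if unadjusted (groups of 6). Note that these are large-sample figures with equal group sizes.
4. Keep 248.
5. Use the same one-arm formula in the re-calculation described under Stopping rules, and state the group size it uses.

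The cost is protocol wording, with no change to recruitment or data collection. Step 2 needs a decision on the primary model, which should be made before outcome data are seen by arm.
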